
**Table 7. Specific Toxicity Management Guidelines for Abnormal Laboratory Values (Continued)**

Laboratory Parameter	Toxicity Management Guideline
Serum Creatinine	
 
If serum creatine is <math>> 1.5 \times</math> the baseline value and <math>></math> ULN, repeat the test for serum creatinine (with subject in an euvolemic state) to confirm the results. If the results of the repeat testing still meet this criterion, then interrupt study drug and re-start study drug once serum creatinine returns to <math>\leq 1.5 \times</math> baseline value and <math>\leq</math> ULN.
 
If confirmed serum creatinine <math>\geq 2</math> mg/dL, interrupt study drug and re-start study drug once serum creatinine returns to normal reference range or its baseline value.
 
 
For the above serum creatinine elevation scenarios, complete supplemental renal eCRF.

Creatine Phosphokinase	
 
If confirmed CPK value <math>\geq 4 \times</math> ULN and there are no symptoms suggestive of myositis or rhabdomyolysis, the subject may continue study drug at the investigator's discretion.
 
If CPK <math>\geq 4 \times</math> ULN accompanied by symptoms suggestive of myositis or rhabdomyolysis, interrupt study drug and contact AbbVie TA MD.
 
 
For the above CPK elevation scenarios, complete supplemental CPK eCRF.

For allowed study drug interruption, the following rules apply:

### Period 1

- Allow study drug interruption up to 7 consecutive days for AEs and emergency surgery. Elective surgery will not be allowed during the first 12-week period.
- If the subject must undergo emergency surgery, the study drug should be interrupted at the time of the surgery. Allow reintroduction of study drug once the physician has examined the surgical site and determined that it has healed and there is no sign of infection.

### Period 2

- Allow study drug interruption up to 7 consecutive days for AEs and emergency surgery during Week 12 to Week 24 in Period 2 and after Week 24 and thereafter, up to 30 consecutive days of study drug interruption is allowed.

- If the subject undergoes elective surgery, the study drug should be interrupted 1 week prior to the planned surgery. Allow reintroduction of study drug once the physician has examined the surgical site and determined that it has healed and there is no sign of infection.
- If the subject must undergo emergency surgery, the study drug should be interrupted at the time of surgery. Allow reintroduction of study drug once the physician has examined the surgical site and determined that it has healed and there is no sign of infection.

### **6.1.8                   Data Monitoring Committee**

An external DMC will review unblinded safety data. See Section [5.5.5.2](#).

### **6.1.9                   Cardiovascular Adjudication Committee**

An independent committee of physician experts in cardiovascular adjudication will be utilized to assess potential cardiovascular AEs in a blinded manner as defined by the Cardiovascular Adjudication Committee charter.

## **6.2                      Product Complaint**

### **6.2.1                   Definition**

A Product Complaint is any Complaint (see Section [6.0](#) for the definition) related to the biologic or drug component of the product.

For a product this may include, but is not limited to, damaged/broken product or packaging, product appearance whose color/markings do not match the labeling, labeling discrepancies/inadequacies in the labeling/instructions (example: printing illegible), missing components/product, or packaging issues.

Any information available to help in the determination of causality to the events outlined directly above should be captured.

### **6.2.2 Reporting**

Product Complaints concerning the investigational product must be reported to the Sponsor within 1 business day of the study site's knowledge of the event via the Product Complaint form. Product Complaints occurring during the study will be followed-up to a satisfactory conclusion. All follow-up information is to be reported to the Sponsor (or an authorized representative) and documented in source as required by the Sponsor. Product Complaints associated with adverse events will be reported in the study summary. All other complaints will be monitored on an ongoing basis.

Product Complaints may require return of the product with the alleged complaint condition. In instances where a return is requested, every effort should be made by the Investigator to return the product within 30 days. If returns cannot be accommodated within 30 days, the site will need to provide justification and an estimated date of return.

The description of the complaint is important for AbbVie in order to enable AbbVie to investigate and determine if any corrective actions are required.

## **8.0                    Statistical Methods and Determination of Sample Size**

### **8.1                    Statistical and Analytical Plans**

An unblinded analysis will be conducted after all subjects have completed Period 1 (Week 12) and additional unblinded analyses for the purpose of regulatory submission

will be conducted. Study sites and subjects will remain blinded for the duration of the study.

Completed and specific details of the statistical analysis will be described and fully documented in the Statistical Analysis Plan (SAP). The SAP will be finalized prior to the Week 12 database lock. The statistical analyses will be performed using SAS (SAS Institute Inc., Cary, NC, USA).

### **8.1.1                   Analysis Populations**

#### **8.1.1.1               Full Analysis Set (FAS)**

The Full Analysis Set (FAS) includes all randomized subjects who received at least one dose of study drug. The FAS will be used for all efficacy and baseline analyses.

#### **8.1.1.2               Per Protocol Analysis Set**

The Per-Protocol Analysis Set represents a subset of the FAS and consists of all FAS subjects who did not meet any major protocol violations during the study. Definitions of major protocol violations will be detailed in the SAP. Additional analysis may be conducted on the Per Protocol analysis set, in order to evaluate the impact of major protocol violations.

#### **8.1.1.3               Safety Analysis Set**

The Safety Analysis Set consists of all subjects who received at least one dose of study drug. For the Safety Analysis Set, subjects are assigned to a treatment group based on the treatment actually received, regardless of the treatment randomized.

### **8.1.2                   Subject Accountability, Disposition and Study Drug Exposure**

#### **8.1.2.1               Subject Accountability**

The following will be summarized by site and by treatment group as well as overall separately for Period 1 and Period 2: number of subjects randomized, the number of

subjects who received at least one dose of study drug, the number of subjects who completed the study, and the number of subjects who prematurely discontinued.

#### **8.1.2.2            Subject Disposition**

Separately for Period 1 and Period 2, the number and percentage of subjects who are randomized, received at least one dose of study drug, prematurely discontinued, and completed the study will be summarized by treatment group and overall. Reasons for premature discontinuation of study drug will be summarized for all randomized subjects by treatment group and overall, with frequencies and percentages by reason for discontinuation.

#### **8.1.2.3            Study Drug Exposure**

Exposure to study drug will be summarized for the Safety Analysis Set Period 1 alone as well as for Period 1 and Period 2 combined. The exposure to study drug (days) will be summarized with the mean, standard deviation, median, and range for each treatment group. The exposure to study drug is defined as the difference between the dates of the first and last doses of the study drug plus 1 day.

Study drug compliance will be summarized for each treatment group for Period 1. The compliance is defined as the number of tablets taken (i.e., the difference between the number of tablets dispensed and the number of tablets returned) during the subject's participation in Period 1 divided by the number of tablets a subject is supposed to take each day times the length of time that the subject was in the treatment phase of Period 1.

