### **8.1.5.2.1 Treatment-Emergent Adverse Events (TEAE)**

AEs will be coded using MedDRA. A TEAE is defined as AE that began or worsened in severity after initiation of study drug.

AEs starting more than 30 days following the last dose of study drug will not be included in summaries of TEAEs. For subjects who continued into Period 2, the AEs that are reported in Period 2 will be captured in the combined safety analysis of Period 1 and Period 2.

As a general safety summary, the number and percentage of subjects experiencing TEAEs will be summarized for each treatment group for the following AE categories:

- All AEs;
- All severe AEs;
- All reasonably possibly related AEs;
- All SAEs;
- Frequent AEs (reported in 5% of subjects or more in any treatment group);
- Frequent reasonably possibly related AEs (reported in 5% of subjects or more in any treatment group);
- Discontinuations due to AEs;
- Death.

Additional AEs may be considered for tabulation/summary based on recommendations from Clinical and Safety as deemed appropriate.

TEAEs will be summarized and presented by system organ classes (SOCs) and preferred terms (PTs) using MedDRA. The SOCs will be presented in alphabetical order, and the PTs will be presented in alphabetical order within each SOC.

TEAE will also be summarized by maximum severity and by maximum relationship.

The AEs of special interest (including but not limited to serious infection, opportunistic infection, malignancy, non-melanoma skin cancer (NMSC), malignancy other than NMSC, lymphoma, hepatic disorder, gastrointestinal perforation, anemia, neutropenia, lymphopenia, herpes zoster, increased CPK, renal dysfunction, tuberculosis, adjudicated cardiovascular events and embolic and thrombotic events (non-cardiac, non-CNS) will be summarized. Event rate (per 100 patient years) for AEs of special interest will also be summarized for the combined safety analysis of Period 1 and Period 2.

All AEs leading to discontinuation of study drug will be presented in listing format. A listing by treatment group of TEAEs grouped by SOC and MedDRA preferred term with subject identification numbers will be generated.

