10.2 Analysis of Adverse Events

10.2.1 Treatment-Emergent Adverse Events

A treatment-emergent Adverse Event (TEAE) is defined as an adverse event with an onset date that is after the first dose of study drug, and no more than 30 days of the drug after the last dose of study drug.

Events where the onset date is the same as the study drug start date are assumed to be treatment-emergent, unless the study drug start time and the adverse event start time are

collected and the adverse event start time is prior to the study drug start time. If an incomplete onset date was collected for an adverse event, the event will be assumed to be treatment-emergent unless there is other evidence that confirms that the event was not treatment-emergent (e.g., the event end date was prior to the study drug start date).

Adverse event data will be presented by SOCs and PTs using MedDRA version 19.0 or most up to date version. All adverse event tables will be sorted in alphabetical order by SOC and PT and descending percentages for each treatment group.

10.2.2 Analysis of Adverse Events for Period 1

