10.2.3 Analysis of Long Term Adverse Event Rates

Long term adverse event rates will be analyzed using event rates adjusted by cumulative exposure and will be based on the actual treatment received at the time of AE occurrence. The detailed treatment groups are defined as follows.

1. Upadacitinib (ABT-494) 7.5 mg QD

This includes AEs occurred under Upadacitinib 7.5 mg QD exposure from subjects starting on Upadacitinib 7.5 mg QD and subjects switching from placebo to Upadacitinib 7.5 mg QD.

2. Upadacitinib (ABT-494) 15 mg QD

This includes AEs occurred under Upadacitinib 15 mg QD exposure from subjects starting on Upadacitinib 15 mg QD and subjects switching from placebo to Upadacitinib 15 mg QD.

3. Upadacitinib (ABT-494) 30 mg QD

This includes AEs occurred under Upadacitinib 30 mg QD exposure from subjects starting on Upadacitinib 30 mg QD and subjects switching from placebo to Upadacitinib 30 mg QD.

4. Placebo

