10.2.3.1 Overview of Adverse Events Rates per 100 Patient-Years of Study Drug Exposure

An overview of AEs per 100 patient-years of study exposure will be presented by treatment group and overall for the following AE categories.

- All TEAEs
- Treatment-emergent serious adverse events (SAEs)
- Treatment-emergent severe adverse events

- TEAEs reasonably possibly related to study drug
- TEAEs of special interest
- TEAEs leading to discontinuation of study drug
- TEAE leading to death

For this calculation, 1 year will be considered to be 365.25 days. For each treatment group, the numerator of the overall rate will be the total number of TEAEs reported for the event; that is, a subject can contribute more than one event to the numerator. For each treatment group, the denominator of the rates will be the total number of days exposed to study drug summed across all treated subjects divided by 365.25. Please refer to Section 8.0 for the calculation of study drug exposure. The AE rate per 100 patient-years of exposure will be calculated as $([\text{numerator}/\text{denominator}]) * 100$. The number of AEs reported (numerator), the total number of years of study drug exposure (denominator), and the AE rate per 100 patient-years will be presented for each treatment group and overall.

Additional AEs may be considered for tabulation/summary based on recommendations from Clinical and Safety as deemed appropriate.

For TEAEs of special interest, the point estimate and 95% CI (using normal approximation) will be provided for the treatment difference in AE rate per 100 patient-years between each Upadacitinib dose group and the combined placebo group.

10.2.3.2 Adverse Events Rates per 100 Patient-Years of Study Drug Exposure by SOC and PT

For each treatment group, the TEAE rate per 100 patient-years of exposure will be calculated overall, for each SOC and each PT, for each of the following events:

- All TEAEs
- Treatment-emergent serious adverse events (SAEs)
- Treatment-emergent severe adverse events
- TEAEs reasonably possibly related to study drug
- TEAEs leading to discontinuation of study drug

- TEAE leading to death
- TEAEs of special interest

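### Long-term adverse-event rates count events up to 30 days after the last dose but divide by first-to-last-dose days, so each rate is overstated by a small amount that depends on drop-out and data cut-off

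*Protocol*

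**What the plan says.** **Numerator.** SAP 10.2.3.1 states that "the numerator of the overall rate will be the total number of TEAEs reported for the event", and repeat events in one subject all count. SAP 10.2.3.2 and 10.2.3.3 use the same rule by system organ class, preferred term and AESI. SAP 10.2.1 lets a TEAE start "no more than 30 days of the drug after the last dose of study drug". Protocol 8.1.5.2.1 sets the same limit: "AEs starting more than 30 days following the last dose of study drug will not be included in summaries of TEAEs".

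**Denominator.** SAP 10.2.3.1 says "the denominator of the rates will be the total number of days exposed to study drug summed across all treated subjects divided by 365.25" and adds "Please refer to Section 8.0 for the calculation of study drug exposure". SAP 8.0 lists treatment groups and cumulative duration bands but contains no formula. The only formula is in Protocol 8.1.2.3, where exposure is "defined as the difference between the dates of the first and last doses of the study drug plus 1 day". It has no 30-day extension and no rule for dividing a placebo subject's exposure at the Week 12 switch, although the groups in SAP 8.0 show that such a split is intended.

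**Allocation and use.** SAP 10.2.3 says the long-term rates "will be based on the actual treatment received at the time of AE occurrence". For AESIs, SAP 10.2.3.1 plans a point estimate and 95% CI for the "treatment difference in AE rate per 100 patient-years between each Upadacitinib dose group and the combined placebo group".

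**The concern.** A rate per patient-year needs the same window above and below the line. Here a subject who stops can contribute events for up to 30 further days that add nothing to patient-years. Those events will be collected: Protocol 6.1.4 gathers adverse events until 30 days after study drug stops, and Protocol 5.1 schedules a follow-up visit or call at about that time.

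The size of the effect depends on how many subjects have stopped and on how much exposure has accrued. It can therefore differ between dose groups, between placebo and upadacitinib, and between one data cut and the next. A reader of the tables cannot correct for it.

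The allocation rule adds a second gap. An event that starts after the last dose occurs while no treatment is being received. One programmer could drop it and another could charge it to the last treatment, and both could claim to follow the SAP.

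**Working it through.** The documents give no event rate or patient-year total, so there is no plan figure to reproduce.

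**Inputs from the documents**
- 48 subjects start each upadacitinib dose, 16 placebo subjects switch to it at Week 12, and there are 48 placebo subjects in all (Protocol 5.1).
- Placebo dosing lasts about 84 days, because the last Period 1 dose is the day before the Week 12 visit (SAP 4.2).
- The design drop-out is 5% (Protocol 8.2, SAP 4.3), used here as the Period 1 rate.
- Dosing is expected to last about 3.5 years, i.e. 1,278 days (Protocol 5.6.4).
- The post-dose window is 30 days.

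**Assumptions not in the documents**
- The event rate is the same on drug and in the 30 days after.
- Period 2 drop-out is 5–40%, spread evenly over time.
- Period 1 drop-outs leave on average at day 42.

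**Formula.** Relative overstatement = (post-dose days at risk) / (first-to-last-dose days).

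**Upadacitinib, all 64 subjects treated to the end, then stopped**
- Unmatched time: 64 × 30/365.25 = 5.26 PY.
- Counted time at *y* years: 48*y* + 16(*y* − 84/365.25).
- 3.5 years: 5.26/220.3 = 2.4%. 2 years: 5.26/124.3 = 4.2%. 1 year: 5.26/60.3 = 8.7%.

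**Upadacitinib, 3.5 years, 5% Period 1 and 20% Period 2 drop-out**
- Period 1 drop-outs: 2.4 × 42 = 101 days.
- Other starters (45.6): 9.12 × 681.2 + 36.48 × 1,278.4 = 52,848 days.
- Switchers (15.2): 3.04 × 597.2 + 12.16 × 1,194.4 = 16,339 days.
- Total: 69,287 days, or 190 PY.
- Final analysis: (2.4 + 45.6 + 15.2) × 30 = 1,896 days, and 1,896/69,287 = 2.7%.
- Data cut with the rest still on drug: (2.4 + 9.12 + 3.04) × 30 = 437 days, and 437/69,287 = 0.6%.

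| Period 2 drop-out | PY at 3.5 years | Final analysis | Cut, subjects ongoing |
|---|---|---|---|
| 5% | 205 | 2.5% | 0.2% |
| 10% | 200 | 2.6% | 0.4% |
| 20% | 190 | 2.7% | 0.6% |
| 40% | 170 | 3.1% | 1.3% |

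**Placebo, 5% Period 1 drop-out**
- Counted time: 45.6 × 84 + 2.4 × 42 = 3,931 days, or 10.8 PY.
- Unmatched time: 2.4 × 30 = 72 days, and 72/3,931 = 1.8%.
- At 2%, 10% and 15% drop-out the result is 0.7%, 3.8% and 5.8%.

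**Net effect on the comparison**
- Final analysis, 20% Period 2 drop-out: the rate ratio is multiplied by 1.027/1.018 = 1.009.
- If both true rates were 10 per 100 PY (assumed), the difference shifts by 10 × (0.0274 − 0.0183) = +0.09 per 100 PY.
- At the data cut it shifts by 10 × (0.0063 − 0.0183) = −0.12 per 100 PY, so the sign reverses.

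**The case against.** Four arguments can be made for leaving the text alone.

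1. **The numerator can be read more narrowly.** SAP 10.2.3 describes each group as events that arose under that dose's exposure. On that reading post-dose events drop out and the windows match. This shows that the text is ambiguous, but it does not remove the conflict: SAP 10.2.1 defines TEAEs to 30 days, and 10.2.3.1 puts all of them in the numerator. The narrow reading would also discard events that begin soon after stopping.
2. **The label is open.** The headings say patient-years of study drug exposure. That is a fair description of the denominator, but it does not tell the reader that the numerator runs longer.
3. **The effect is small against the precision available.** With about 10.8 placebo PY, one event moves the placebo rate by 100/10.8, or about 9 per 100 PY, against shifts of about 0.1 in the examples above. This stands. In addition, first-to-last-dose exposure includes interruption days, which pushes rates down.
4. **The randomised comparison is untouched.** SAP 10.2.2.1 compares Period 1 AESIs as percentages of subjects. This also stands.

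A stronger reading is tempting: since placebo subjects who enter Period 2 switch at once and have no post-dose window, the placebo rate is spared and the difference is biased against upadacitinib by construction. The figures do not support that. Few placebo subjects have a tail, but a 30-day tail is 30/84 = 36% of a full placebo course against 30/1,278 = 2.3% of 3.5 years. The small placebo denominator makes the two overstatements similar in size.

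**Conclusion.** The mismatch between numerator and denominator is in the text, as are the missing formula in SAP 8.0 and the missing rule for events after the last dose. At the planned duration the bias is a few percent at most: about 2.4–3.1% for an upadacitinib dose group at a 3.5-year final analysis, 0.2–1.3% at a 3.5-year cut with subjects ongoing, and about 1.8% for placebo at 5% Period 1 drop-out. The figures of about 4% at 2 years and 9% at 1 year require every subject to have stopped by then, which is not the plan.

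The direction of the net bias in the dose-versus-placebo AESI rate difference depends on drop-out, cut-off and the underlying rates, so no fixed direction should be claimed. All of this rests on an equal event rate on drug and in the 30 days after, and on the assumed Period 2 drop-out. Events that cluster after a stop for toxicity would make the overstatement larger. No conclusion of the trial is likely to turn on this, but these are its main long-term safety rates and the correction is cheap.

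**What to change.** In SAP 8.0 and 10.2.3:

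- State a formula per treatment for the rate denominator: days from the first dose of that treatment to the earliest of last dose + 30 days, the day before the switch to upadacitinib (placebo subjects), last contact, or data cut-off.
- Assign TEAEs that start after the last dose to the last treatment received.
- Keep first-to-last-dose days for the exposure-duration table only.

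Numerator and denominator then cover the same time, and the overstatement calculated above falls to zero in every group.

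The cost is a few lines of SAP text and a small programming change. Reported patient-years rise slightly: in the 20% drop-out example at final analysis, by 1,896/365.25 = 5.2 PY on 190 for a dose group, and by 72/365.25 = 0.2 PY on 10.8 for placebo. They are then no longer pure drug exposure, so the table labels must say that they are time at risk including up to 30 days after the last dose.

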#### **8.1.3                Analysis of Demographic and Baseline Characteristics**

Demographic and baseline characteristics will be summarized by treatment group and overall for the FAS. For the purpose of this analysis, baseline data for each subject will be the data collected immediately prior to the first dose of study drug in Period 1.

Summary statistics for continuous variables will include the number of observations, mean, standard deviation, median, and range. For discrete variables, frequencies and percentages for each category will be summarized.

Medical history will be presented by counts and percentages of subjects, broken down by Body System and Diagnosis.

Prior therapy and medication will be summarized by treatment group. Prior therapy and medication will include all therapies and medications with a start date prior to the date of first dose of study drug.

Concomitant medications will also be summarized with frequencies and percentages for each treatment group. All medications administered during study drug exposure will be included.

